Appendix 1.0: Time and Events Schedule

Visit type Procedure	Visit 1*	Visit 2	Visit 3	Visit 4	Visit 5	Visit 6
	Screening Baseline Measures	Tx1 (same day or within 21 days after screening)	Tx2 (14 days after Tx1 +/- 2 days)	Tx3 (14 days after Tx2 +/- 2 days)	1 Month Follow-up (30 days after Tx3 +/- 7 days)	3 Month Follow- up (90 days after Tx3 +/- 10 days)
Medical History and Demographics	√					
Physical Exam	√					
Skin type	√					
Pregnancy Screening	√	√	√	√		√
Inclusion/Exclusion Criteria	√					
Informed Consent	√					
Photos	√				√	√
BMI/Height/Weight	√		√	√	√	√
Circumference	√		√	√	√	√
Caliper	√		√	√	√	√
Ultrasound	√					√
Histology-8 subjects (At selected sites)	√					√
Treatment		√	√	√		
Subject's Comfort		√	√	√		
Subject's Satisfaction						√
Skin response and AE		√	√	√	√	√
Concomitant Medication	√	√	√	√	√	√
Study End						√

* Screening and 1st treatment may occur on the same day and up to 3 weeks interval

	Safety and Efficacy of Trim II for Non-invasive Lipolysis and Circumference Reduction of Abdomen.	
	Protocol No: DO609924A SIRB ID: 8659	Rev. Date: Jun 3 2022

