8.4 Visit 5: Follow-up visit – 3 months following last treatment

- Treatment area will be photographed
- Pregnancy Urine Test prior to the treatment
- Weight and height (BMI calculation)
- Circumference tape measurement
- Caliper measurement
- Abdominal fat thickness measured by ultrasound
- Histologies (8 subjects)
- Subject's satisfaction

After each treatment and at all visits, any adverse events will be recorded.

	Safety and Efficacy of Trim II for Non-invasive Lipolysis and Circumference Reduction of Abdomen.	
	Protocol No: DO609924A SIRB ID: 8659	Rev. Date: Jun 3 2022

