9.1 Definitions

Adverse Event:

An adverse event (AE) is any adverse change in health or side effect that occurs in a study participant during their participation in the study.

Serious Adverse Event (SAE):

A serious adverse event (SAE) is any adverse event that:

- Led to death
- Led to a serious deterioration in the health of the subject that resulted in a life-threatening illness or injury
- Resulted in a permanent impairment of a body structure or a body function
- Required in-subject hospitalization or prolongation of existing hospitalization

	Safety and Efficacy of Trim II for Non-invasive Lipolysis and Circumference Reduction of Abdomen.	
	Protocol No: DO609924A SIRB ID: 8659	Rev. Date: Jun 3 2022

- Resulted in medical or surgical intervention to prevent permanent impairment to body structure or a body function
- Led to fatal distress, a congenital abnormality, birth defect or death

Unanticipated Adverse Event:

An unanticipated adverse event is any serious, device-related adverse event, if that event was not previously identified in the risk analysis and Informed Consent form in nature, severity, or frequency.

AE Severity:

Adverse events are graded according to severity as follows (Table 2):

Mild	Sign or symptom, usually transient, requiring no special treatment and generally not interfering with usual activities.
Moderate	Sign or symptom, which may be ameliorated by simple therapeutic measures; yet, may interfere with usual activity.
Severe	Sign or symptom that are intense or debilitating and that interfere with usual activities. Recovery is usually aided by therapeutic measures.

Relationship to Device:

The relationship of the adverse event to the treatments or procedures is defined as follows (Table 3):

Most Probably Related:	Follows a reasonable temporal sequence from study device delivery/retrieval and cannot be reasonably explained by known characteristics of the subject's clinical data or the surgical procedure applied.
Possibly Related:	Follows a reasonable temporal sequence from study device delivery/retrieval but could have been produced by the subject's clinical state or by the surgical procedures regardless of the study device.
Probably not Related:	Temporal association is such that the study device is not likely to have had any reasonable association with the observed event.
Unrelated	No relationship to study device activation is perceived

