14.1 Analysis Sets

- Safety Analysis Set

The safety analysis set will include all subjects using Embrace procedures at least a single time.

- Performance Analysis Set

Performance analysis set will consist of all subjects providing at least one post treatment performance measurement.

- Treatment of Missing Values

Only observed data will be used; i.e. missing data will not be imputed.

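### The second biopsy is taken at the Study End visit with no adverse-event contact afterwards, and the schedule's AE row omits Visit 1, contrary to the text

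*Combined protocol and SAP*

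**What the plan says.** Visit numbers below are those of Appendix 1.0, which has six visits. Section 8 combines screening and first treatment, so its Visit 5 is Visit 6 in the appendix.

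- **Biopsies.** Appendix 1.0 ticks "Histology-8 subjects (At selected sites" at Visit 1 (screening and baseline) and Visit 6 (3-month follow-up). Section 8.4 lists "Histologies (8 subjects" among the procedures of that last visit. The Study Duration row of the synopsis gives 8-10 biopsied subjects. The synopsis visit list, sections 8.1 and 8.4, Table 1 in section 8.5 and Appendix 1.0 give 8.
- **End of study.** Appendix 1.0 ticks Study End at Visit 6 only. No later visit or call appears in the documents.
- **AE collection in the schedule.** The row "Skin response and AE" is ticked at Visits 2 to 6 and left blank at Visit 1.
- **AE collection in the text.** The synopsis visit list and section 8.4 want AEs recorded at every visit. Section 6.1 makes safety a primary endpoint, with AEs followed for the entire study. Section 9.4 has AEs reported over the study and its follow-up period, and section 12.4 ties AE monitoring to the study visits.
- **AE definition.** Section 9.1 counts an adverse change in health "that occurs in a study participant during their participation in the study". It is not limited to device effects.
- **Known AEs.** Section 9.5 has the investigator keep monitoring an AE until it resolves, stabilises or returns to baseline.
- **Safety set.** Section 14.1: "The safety analysis set will include all subjects using Embrace procedures at least a single time".

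**The concern.** Biopsy is the only invasive procedure that the protocol lists; the others are urine tests, tape, caliper, ultrasound, photographs and questionnaires. The samples come from the treated area. The synopsis also makes the absence of adverse skin events part of the histology success criterion.

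The second biopsy is taken on the day the subject leaves the study. A reaction that begins after that day has no planned occasion on which anyone asks about it. The follow-until-resolved rule in section 9.5 needs an AE that has already been identified. If the final report stated that there were no biopsy-site complications, it could not separate absence from non-observation for the second biopsies, and a subject with a late problem would have no planned contact.

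A smaller matter arises at the first biopsy. The schedule and the text disagree on whether AEs are recorded at Visit 1, and the answer matters most for a subject who is biopsied there and does not return.

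**Working it through.** The plan states no figure on this point. The check reads the schedule row by row, then adds up the visit windows.

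**1. Time covered after the first biopsy.** The inputs are the windows in Appendix 1.0: "Tx1 (same day or within 21 days after screening", "Tx2 (14 days after Tx1 +/- 2 days", "Tx3 (14 days after Tx2 +/- 2 days", the 1-month visit at 30 ± 7 days after Tx3, and the 3-month visit at 90 ± 10 days after Tx3. Days are counted from Visit 1.

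| AE-ticked visit | Minimum | Nominal, Tx1 same day | Nominal, Tx1 at day 21 | Maximum |
|---|---|---|---|---|
| Visit 2 (Tx1) | 0 | 0 | 21 | 21 |
| Visit 3 (Tx2) | 12 | 14 | 35 | 37 |
| Visit 4 (Tx3) | 24 | 28 | 49 | 53 |
| Visit 5 (1 month) | 24 + 23 = 47 | 58 | 79 | 53 + 37 = 90 |
| Visit 6 (3 months) | 24 + 80 = 104 | 118 | 139 | 53 + 100 = 153 |

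So five AE-ticked visits follow the Visit 1 column. The first is 0 to 21 days after the biopsy. If Tx1 is on the same day, the next one is 12 to 16 days later. Scheduled AE observation after the first biopsy lasts 104 to 153 days.

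**2. Time covered after the second biopsy.** AE-ticked visits after Visit 6: 0. Scheduled observation beyond the visit itself: 0 days. The AE tick at Visit 6 could record an immediate reaction if the assessment follows the biopsy, but the order is not given.

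**3. Share of biopsies affected.** Two biopsies per subject:

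- 8 subjects: 2 × 8 = 16 biopsies, 8 of them at Visit 6 (8/16 = 50%).
- 10 subjects: 2 × 10 = 20 biopsies, 10 of them at Visit 6 (10/20 = 50%).

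Against the minimum of 70 subjects, those biopsied are 8/70 = 11.4% to 10/70 = 14.3%.

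**4. Visit 1 in the table and in the text.** The AE row is blank at Visit 1, yet the synopsis and section 8.4 ask for AE recording at every visit. Section 8.1 has an explicit AE step, but places it after treatment. When screening and Tx1 share a day, that step falls on the day of the baseline biopsy. When they are up to 21 days apart, section 8.1 has no explicit AE step on the screening day.

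**5. Biopsied but never treated.** Every later window in Appendix 1.0 is counted from a treatment, except that of Tx1 itself. A subject biopsied at Visit 1 who does not have Tx1 therefore has no further scheduled visit. The safety set requires at least one use of the device, so this subject is not in it.

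**The case against.** **Visit 6 has an AE tick.** Section 8.4 also requires AE recording then, and anything found is followed until it resolves or is stable. This stands for an immediate reaction, provided the assessment comes after the biopsy. It does not reach an event that starts later.

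**Both ends.** A reader might infer that AE collection misses the biopsy at both ends of the study. The documents do not support this. The text requires AE recording at every visit, and a treated subject has five AE-ticked visits from Tx1 onward. The blank cell at Visit 1 also partly reflects numbering: the appendix splits into two columns what section 8.1 treats as one visit. At that end, only the inconsistency and the untreated subject remain.

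**Exclusion by definition.** A reader might also infer that a complication after Visit 6 is excluded from being an AE. That goes too far. Study End is an undefined row label, no section says that participation ceases on leaving Visit 6, and section 9.5 has serious events reported once the investigator learns of them, with no cut-off. What can be said is that the end of AE collection is not defined and that no contact is scheduled.

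**Risk.** Sections 9.2 and 13.1 name infection and scar as possible effects of Trim II, not of biopsy. The documents give no biopsy complication rate, so no expected number of missed events can be given. Procedure-related events are still in scope: the AE definition covers any adverse change, and the causality table in section 9.1 allows for a surgical procedure as an alternative cause.

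**Scale.** The untreated case needs screening and Tx1 on different days, plus dropout between them, among 8 to 10 subjects. Such an AE would still be reportable under sections 9.1 and 9.4, and a safety set based on device exposure is ordinary practice. No efficacy endpoint or planned test is affected. All of this stands and keeps the point modest.

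**Conclusion.** The point holds for the second biopsy: half of the planned biopsies, 8 of 16 or 10 of 20, have no scheduled AE observation after the biopsy visit, against 104 to 153 days after the first. At the first biopsy there is a contradiction between schedule and text, and a narrow gap for a subject biopsied but never treated.

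This does not show that any complication would be lost, or that AEs at Visit 6 go unrecorded. It is a low-cost improvement to safety capture in a study with safety as a primary endpoint.

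The conclusion rests on these assumptions:

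- Study End marks the last scheduled contact.
- Every biopsied subject reaches Visit 6; dropouts would lower the number of second biopsies.
- The device named in the safety set definition is read as Trim II. That name is a separate matter to correct.
- The consent form was not available, so any biopsy aftercare instruction in it could not be weighed.

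**What to change.** - **Appendix 1.0.** For biopsied subjects, add one scheduled contact after the final biopsy, with AE questions about the biopsy site, and move Study End to it. Telephone is enough; the sponsor sets the interval.
- **Sections 9.1 and 9.4.** State that AE collection for these subjects runs to that contact.
- **Visit 1.** Reconcile the blank AE cell with the text that asks for AE recording at every visit, for example by adding the tick.
- **Section 14.1.** Keep the safety set based on device exposure, and list AEs in any biopsied but untreated subject separately beside it.
- **Number biopsied.** Reconcile 8-10 with 8, so that the number of contacts is known.

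The cost is 8 to 10 calls, some protocol wording and a slightly later study end for these subjects. Treatment, endpoints and sample size do not change.

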Appendix 2.0. Measuring Fat Thickness at the Treated Area using Ultrasound Imaging (USI) Device

- At screening visit, the therapist will mark the rectangle of the treatment area according to the applicators setting with white pencil.
- Two US measurement points will be selected and images will be captured (according to the applicators positioning)
- A transparency will be created at baseline for each patient, with treated area, identification marks (umbilicus, spots/moles) and the measurements points marked, to ensure USI of the same point at baseline and FU visit.
- US probe should be applied to measure abdominal subcutaneous fat in the area of the two measurement points (identified according to the transparency).
- Each measurement of fat later thickness should be repeated 2 times and an average value will be recorded.

	Safety and Efficacy of Trim II for Non-invasive Lipolysis and Circumference Reduction of Abdomen.	
	Protocol No: DO609924A SIRB ID: 8659	Rev. Date: Jun 3 2022

Appendix 3.0: Photography

At each of the specified time points; photographs of the treated areas should be taken by investigator or their designee.

- Photographs should be taken in a private room or area of the clinic under controlled conditions, including the distance from the camera to the subject, height of the camera, background, camera positioning, subject's positioning and lighting in order to achieve high-quality before & after sets.
- Consistent lighting- Lighting should be preferably projected from about 45° angle in order to emphasize the treatment area appearance.
- For consistency purposes, the same person should ideally take all study photographs.
- The digital files should follow a consistent standard naming scheme containing subject initials and study ID #, visit or visit date.

Specific photography details:

Area: Abdomen:

Five photographs should be taken at each specified time point

- Front
- 45° from the right side
- 90° from the right side
- 45° from the left side
- 90° from the left side

The subject's arms should remain out of the way; it is best to either cross them over each other in front of the chest or hold them up at a 90° angle to the body, ensuring that they do not rest on the chest or touch the body and that they do not cast a shadow in the photograph.

	Safety and Efficacy of Trim II for Non-invasive Lipolysis and Circumference Reduction of Abdomen.	
	Protocol No: DO609924A SIRB ID: 8659	Rev. Date: Jun 3 2022

Appendix 4.0: Circumference Measurements

The following steps are necessary to achieve consistent measurements:

- The measurement tape should be parallel to the floor during the measurement
- Prior to circumference measurement, mark the area to be treated in order to perform the measurements within the defined area for treatment. The area to be measured must be at height that includes the area to be treated.
- Baseline measurement should be taken at the level of the widest part of area (most protruding convexity) – horizontal midline. This height level should be recorded for follow up assessments. Two additional measurements will be taken at 2 inches/5cm above this baseline and 2 inches/5 cm below it.
- The consecutive measurements should be performed at the same height recorded at enrollment. In order to assure that measuring tape is parallel to the floor, several reference points should be marked around the treatment area and the measuring tape should be placed such that it is aligned with them.
- The tape should be placed under the reference points in order to maintain repetitive height of the measurement
- The measurement device should be placed at a constant tension to achieve an exact measurement of the circumference
- The same trained evaluator will preferably perform the circumference measurement to avoid bias in results. In case that evaluator is not available, another trained person will perform the procedure.

The circumference measurement:

- Position the subject next to a fixed height measuring device. Such a device could be a wooden/metal measurement stick, fixed perpendicular to the floor.
- Alternatively, a medical height measuring device will be employed.
- The height reference line should be at the widest part of the marked treatment area (horizontal mid-line).
- This height should be kept as the reference in the follow up throughout all measurements of the same treatment area.
- In order to ensure a reproducible posture, position the subject as close as possible to the measurement stick.
- Arms will be crossed over the chest with hands placed in the opposite axillae. The head will be held up with eyes level and looking straight ahead.

I N M O D E

Safety and Efficacy of Trim II for Non-invasive Lipolysis and Circumference Reduction of Abdomen.

Protocol No: DO609924A SIRB ID: 8659

Rev. Date: Jun 3 2022

- Have the subject rotate slowly to produce the height reference line. This line should be marked on the skin as the subject rotates. Make sure that the height reference points cover the entire length of the circumference, at front, back and two sides.
- In the subject file, record the height of the horizontal mid-line of the treatment area (the distance from the floor). This will enable the operator to re-measure the subject at the same height in the follow up visits for the evaluation of the change in the circumference.
- Place the measurement tape at the widest part of the marked area. The measurement tape should be placed below the reference line.
- Record the measured circumference in the subject file
- Measure circumference at 2 inches/5 cm above the horizontal midsection of the marked treatment area
- Measure circumference at 2 inches/5 cm below the horizontal midsection of the marked treatment area.

I N M O D E

Safety and Efficacy of Trim II for Non-invasive Lipolysis and Circumference Reduction of Abdomen.

Protocol No: DO609924A SIRB ID: 8659

Rev. Date: Jun 3 2022

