6.1 Primary Endpoints

- Efficacy of the Trim II treatment for lipolysis and abdominal circumference reduction.
Evaluation of change in abdomen circumference using tape measurements in cm at the 3 months follow-up visit comparing to baseline.
Success criteria: Statistically significant reduction in abdominal circumference tape measurements at the 3 months follow-up visit compared to baseline.
* The primary effectiveness endpoint will be calculated based on those patients whose weight remains stable during the study period. A subject is defined as having maintained her weight during the treatment period if it remained within $\pm 3\%$ (inclusive) of baseline for the respective period.

 I N M O D E	Safety and Efficacy of Trim II for Non-invasive Lipolysis and Circumference Reduction of Abdomen.	
	Protocol No: DO609924A SIRB ID: 8659	Rev. Date: Jun 3 2022

- Safety of the Trim II treatment for lipolysis and abdominal circumference reduction. The occurrence of adverse events will be followed throughout the whole study. Observation, assessment and recording of potential reactions by the investigator. Evaluations will be done immediately after each treatment and at the follow-up visits. The frequency, severity and causality of reactions will be recorded.

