7.2 Subject Withdrawal and Replacement

Subjects enrolled in the study can discontinue their participation at any time for any reason without prejudice or reduction in the quality of their medical care. The investigators or sponsor can terminate a

	Safety and Efficacy of Trim II for Non-invasive Lipolysis and Circumference Reduction of Abdomen.	
	Protocol No: DO609924A SIRB ID: 8659	Rev. Date: Jun 3 2022

subject's participation in this study to protect the subject's health or if the subject fails to follow directions resulting in noncompliance to study procedures. Subjects who withdraw or are terminated from the study may be replaced to ensure that at least 70 subjects have completed the study. Subjects who fail to complete the treatment will be replaced and will not be evaluable.

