14.2 Statistical Analysis

[figure not shown]
Means, and standard deviations for each characteristic will be calculated. Paired sample t-test will be computed to assess changes in before treatment and follow-up scores. Statistical significance will be calculated and two-tail significance level of 0.05 will be used.

15. Data Management Plan

Case Report Forms and questionnaires will be retrieved by Monitors after source data verification and resolution of monitoring queries. Documents will be delivered to InMode Ltd onsite data management facility where forms will be logged in, and then data will be entered using a double entry method.

16. References

4. [name], [name] Neuromascular Electrical Stimulation and Strength Recovery

I N M O D E

Safety and Efficacy of Trim II for Non-invasive Lipolysis and Circumference Reduction of Abdomen.

Protocol No: DO609924A SIRB ID: 8659

Rev. Date: Jun 3 2022

of Postnatal Diastasis Recti Abdominis Muscles. Ann Rehabil Med 2017;41(3):465-474 pISSN: 2234-0645 • eISSN: 2234-0653

17. Investigator Study Acknowledgment

Investigator’s Statement:

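### The primary tape measurement has no repeat reading, breathing phase or stated tape edge, although ultrasound readings are duplicated and averaged; precision is lost by an unknown amount

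*Combined protocol and SAP*

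**What the plan says.** Section 6.1 defines the primary efficacy endpoint: "Evaluation of change in abdomen circumference using tape measurements in cm at the 3 months follow-up visit comparing to baseline". Section 14.2 gives the test, "Paired sample t-test will be computed to assess changes in before treatment and follow-up scores", and adds that a "two-tail significance level of 0.05 will be used". Section 7.2 allows replacement so that "at least 70 subjects have completed the study".

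Appendix 4.0 describes the tape measurement. Circumference is read at the widest part of the treatment area and at 5 cm above and below it. The height from the floor is recorded, reference points are marked around the body, arms and head are positioned, and tension is to be constant. On placement, one bullet says "the measuring tape should be placed such that it is aligned with them", and the next says "The tape should be placed under the reference points in order to maintain repetitive height of the measurement". The step list later puts the tape at the widest part and beneath the reference line. On staffing: "The same trained evaluator will preferably perform the circumference measurement to avoid bias in results"; another trained person may step in.

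The appendix does not ask for a second reading at any level, does not say when in the breath to read, and does not say which tape edge meets the marks. Nothing there or in Section 6.1 says which of the three levels, or what combination of them, is the primary value.

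Appendix 2.0, for the secondary ultrasound endpoint, does ask for replication: "Each measurement of fat later thickness should be repeated 2 times and an average value will be recorded".

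**The concern.** Abdominal girth moves with breathing and with small differences in how the tape is laid, so one reading carries error that a second reading in the same session would partly average out. The endpoint is a change score, so that error enters twice, once at baseline and once at 3 months. The consequence is a wider interval and lower power for the same number of subjects. The sponsor already accepts the remedy for ultrasound but does not apply it to the measurement that decides success.

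**Working it through.** **Inputs from the documents.** Paired comparison of baseline with 3 months, two-sided 0.05, single arm, at least 70 completers. Section 6.1 restricts the primary analysis to weight-stable subjects, so the analysed number may be below 70. The ratios below do not depend on n.

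**Inputs not given.** The visible text has no expected reduction, no SD of change and no repeatability figure, so there is no stated figure to reproduce. Assumed: SD of the true change T = 2 cm; within-session error SD of one reading e = 0.5, 1.0 or 1.5 cm, independent between readings.

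**Step 1: one level.** With one reading per visit, Var(change) = T² + 2e². With the mean of two readings per visit, Var(change) = T² + e².

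| e (cm) | Single | Duplicate | SE ratio | SE cut | Equivalent gain in n |
|---|---|---|---|---|---|
| 0.5 | 4 + 0.5 = 4.5 | 4 + 0.25 = 4.25 | √(4.25/4.5) = 0.972 | 3% | 4.5/4.25 = 1.06 |
| 1.0 | 4 + 2 = 6 | 4 + 1 = 5 | √(5/6) = 0.913 | 9% | 6/5 = 1.20 |
| 1.5 | 4 + 4.5 = 8.5 | 4 + 2.25 = 6.25 | √(6.25/8.5) = 0.857 | 14% | 8.5/6.25 = 1.36 |

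In the last row reading error makes up 4.5/8.5 = 53% of the variance of change. Nothing in the documents supports a share that large, so it is the high end of the range.

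**Step 2: the three levels averaged.** Suppose the primary value were the mean of the three levels, with independent errors and a true change common to all three. Then Var = T² + 2e²/3 with single readings and T² + e²/3 with duplicates.

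- e = 0.5: 4.167 against 4.083, SE ratio 0.990, a 1% cut
- e = 1.0: 4.667 against 4.333, SE ratio 0.964, a 4% cut
- e = 1.5: 5.500 against 4.750, SE ratio 0.929, a 7% cut

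On the same assumptions, averaging three single readings improves on one single-read level by SE factors of √(4.167/4.5) = 0.962, √(4.667/6) = 0.882 and √(5.5/8.5) = 0.804. Each is a larger gain than duplicating one level (0.972, 0.913, 0.857).

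**Step 3: effect on power, parameterised differently.** Now hold the SD of the observed change at S = 3 cm with single readings (assumed), and take an illustrative 1 cm reduction with n = 70. Duplicates reduce the variance to S² − e². Power comes from the noncentral t distribution with noncentrality (1/SD)·√70.

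- Single readings: SD 3.000, power 78.5%
- Duplicates, e = 0.3: SD √8.91 = 2.985, power 78.9%
- Duplicates, e = 0.5: SD √8.75 = 2.958, power 79.6%
- Duplicates, e = 1.0: SD √8.00 = 2.828, power 83.1%
- Duplicates, e = 1.5: SD √6.75 = 2.598, power 88.8%

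Both parameterisations agree on direction. The gain runs from negligible to about 10 points of power, depending entirely on an error SD that the documents do not give.

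**The case against.** The strongest reply is that Appendix 4.0 is already a careful procedure: recorded height, skin marks, constant tension, fixed posture and a preferred single evaluator. Duplicates remove only error that differs between two readings in one session. A change of evaluator, or a difference in tape height between visits, is largely shared by both readings and survives averaging. Three levels are already read, and averaging them could recover as much precision or more with no extra readings. Random reading error also makes success harder to show; it does not inflate the claim. All of this stands. It limits the size of the point and explains why the fix must also name the primary value. It does not remove the point: the plan states no rule for combining levels, so that protection cannot be assumed.

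Four stronger readings are tempting, and the documents do not support them.

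- *The placement instructions contradict each other.* A tape whose upper edge follows the marks is aligned with them, under them and beneath the line all at once. The edge is unspecified, which is an ambiguity. A constant offset cancels in the within-subject change.
- *Starting from the widest level biases follow-up readings toward success.* This needs an assumed body profile and an assumed height shift, although height is recorded and marked. With the tape beneath the line, or at the levels 5 cm away, a small shift could read larger or smaller.
- *The primary reading is the least protected one.* Ultrasound has a transparency and duplicate readings, but Appendix 2.0 has no same-evaluator preference. The safeguards differ, and no ranking follows.
- *Calipers are also read twice.* Appendix 6.0 may mean one reading on each side of the umbilicus, so only ultrasound is a clean comparison.

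**Conclusion.** The point holds as an inexpensive improvement to precision. Appendix 4.0 specifies no repeat reading, breathing phase or tape edge for the primary measurement, while Appendix 2.0 duplicates and averages a secondary one. Any nonzero within-session error lowers precision at fixed n. The size cannot be established from the documents. The single-level range (3% to 14% of the standard error) and the three-level range (1% to 7%) both rest on T = 2 cm, e = 0.5 to 1.5 cm and independence between readings; the second also assumes independence across levels. If errors are shared within a session, for example because both readings fall at the same phase of breathing, duplicates gain less. The point does not show that a power target is missed or that the primary result would be biased.

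**What to change.** Amend Appendix 4.0 to apply at every visit:

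1. Read each of the three levels twice, removing the tape between readings, and record the mean.
2. Read at the end of normal expiration.
3. Place the upper edge of the tape directly under the reference line. This sharpens the existing step-list instruction and does not replace it.
4. State that the primary value is the mean of the three levels, or name the single level used, and carry the same statement into Section 6.1.

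The cost is a few minutes per visit and a few lines of text, with no extra staff or equipment. Duplicates will not remove differences between evaluators or between visits. The breathing and tape-edge rules can reduce some of these, and the preference for one evaluator remains useful.
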